5.4. Rationale for Study Design and Dose for Investigational Product

5.4.1. Rationale for Study Design

There are limited clinical data available to support the use of OCA in patients with PBC with moderate to severe hepatic impairment. The current recommended dosing of such patients is based on modeled systemic and hepatic concentrations. Therefore, Study 747-401 is specifically designed to characterize the PK, safety, and efficacy of OCA in this patient population.

PK and safety parameters will be evaluated as the primary objectives and efficacy parameters will be evaluated as secondary and additional objectives. While the prognostic utility of ALP has been established by the Global PBC study group, increasing levels of bilirubin are more relevant to understanding the progression of end stage liver disease. Consistently, bilirubin is a key marker of advancing disease as characterized by the Global PBC study group as well as its incorporation into model of end stage liver disease (MELD), Child-Pugh (CP), and Mayo risk scores. As such, the potential of OCA to stabilize bilirubin levels will be evaluated.

In order to generate data for the patient population in a timely fashion, Study 747-401 is designed with a relatively short-term, 1-year double-blind treatment period to gather primarily PK and safety data. Therefore, the study will not formally test the long-term efficacy of OCA on clinical outcomes.

Although Study 747-401 is not designed to formally evaluate clinical outcomes, these data will be collected and assessed as an additional objective. Given the importance of evaluating clinical outcomes in patients with the most advanced form of the disease, these events will be prospectively adjudicated consistent with the procedures implemented in ongoing PBC studies. This will allow for a more robust meta-evaluation of clinical outcomes in patients with moderate to severe hepatic impairment following the completion of both studies.

Study 747-302 is specifically designed to confirm clinical benefit across the spectrum of disease including patients with hepatic impairment. Data collected from Study 747-401 will serve as a bridge to the 747-302 study.

Taken together, data from this study will complement the data from Study 747-302 and offer the opportunity to better inform the benefit risk profile and appropriate treatment of hepatically-impaired patients.

5.4.2. Rationale for Obeticholic Acid Dose and Duration

Simulations using a physiologic PK model predicted changes in systemic and liver OCA concentrations associated with changes in the severity of hepatic impairment (CP Score). Model simulations predicted that for mild (Child-Pugh A [CP-A]), moderate (Child-Pugh B [CP-B]), and severe (Child-Pugh C [CP-C]) hepatic impairment, total OCA plasma concentrations increase 1.4-, 8.0-, and 13-fold relative to patients with normal hepatic function, whereas total OCA liver concentrations increase 1.1-, 1.5-, and 1.7-fold, respectively. Because the liver is the primary site of action for the safety and efficacy of OCA, it is important to account for the differences in systemic and liver exposure when assessing effective doses. It is also important to note that while hepatically impaired (CP-B and C) patients treated with OCA in Phase 1 and 2 studies experienced plasma OCA exposures >10-fold higher than those in healthy patients, no apparent impact on the overall safety profile was observed, consistent with only a modest

increase in liver exposure of OCA associated with hepatic impairment. Together, the results from these analyses suggest that the doses of OCA administered to patients with moderate or severe hepatic impairment should be modestly lower than those for patients with normal hepatic function to achieve similar hepatic exposure.

Therefore, the current FDA-approved prescribing information for OCA includes a modified dosing regimen in patients with moderate and severe hepatic impairment that is designed to achieve liver exposures in these patients that would be similar to non-hepatically impaired patients through initiation at a lower dose (5 mg OCA once-weekly) followed by gradual up-titration ([Section 7.3](#)).

5.4.3. Rationale for Population Chosen

Patients with PBC and moderate or severe hepatic impairment, based on CP score and varying levels of MELD, are the targeted population for this study as OCA has been studied primarily in early to moderate stages of liver impairment in patients with PBC. There is a great need to extend therapies to PBC patients with more advanced liver impairment. Given the unmet medical need and observed efficacy, safety and tolerability profile of OCA in early and moderate PBC, evaluating the effects of OCA in a late stage population is warranted.

5.4.4. Rationale for Control Group

The use of a randomized placebo control group added to established standard of care provides the best scientific evidence of efficacy and safety. The use of a placebo control provides a concurrent comparator group, accounting for not only a placebo effect but continued standard of care. The use of a placebo control is critical to assess the safety and tolerability of OCA but also as a comparator for the high rate of clinical events which are expected in this advanced population.

5.5. Importance of Monitoring of Disease Progression

Given PBC is a chronic, progressive liver disease, it is important that patients with PBC are closely monitored to ensure early identification of decompensation and/or liver injury. More extensive safety monitoring and appropriate dosing adjustments, interruptions, and discontinuations will be implemented to improve patient oversight and safety. Investigators, together with the Sponsor's Medical Monitor, will consistently and frequently assess individual patients to determine on an ongoing basis the totality of a patient's clinical profile, which includes careful evaluation of signs and symptoms of potential hepatic injury and/or decompensation coupled with rules-based laboratory monitoring.

Patients will be monitored for potential hepatic injury and/or decompensation. Criteria for implementing dosing adjustments, interruptions, or discontinuations, and close monitoring procedures postdose-adjustment are described in [Section 8.4](#) and [Section 7.6](#). The more extensive monitoring is important given the elevated risk of decompensation and potential for higher hepatic exposure to OCA in this population.

5.6. Summary of Known Potential Risks with Investigational Product

The rate of progression and risk of decompensation is variable and may be rapid in certain patients, necessitating closer surveillance of patients at risk.

Clinical Data

In two Phase 2 studies and a Phase 3 study evaluating OCA in the treatment of subjects with PBC, hepatic adverse events were observed in subjects receiving doses of OCA ranging from the maximum approved dose of 10 mg once daily to 50 mg (5 times the highest recommended dose).

Recent safety findings in NASH clinical trials include 2 cases of hepatic decompensation reported as SUSARs, 1 of which resulted in death. Both cases involved numerous confounding factors that make evaluation of association with treatment difficult. Details for both events are provided in the Investigator's Brochure Addendum 1 to Version Number: 16 (31 March 2017), Effective Date: 02 October 2017.

The primary AE shown to be related to OCA is pruritus. Pruritus has also been observed in clinical studies with OCA in other indications, as well as in healthy subjects, with the highest frequency observed in subjects with PBC. The incidence and severity of pruritus have been shown to be dose dependent, but there is no evidence of association with stage or progression of underlying disease.

Changes in lipid profiles have also been observed with OCA dosing, including an increase in low-density lipoprotein (LDL) cholesterol and a decrease in high-density lipoprotein (HDL) cholesterol. The clinical significance of these lipid findings remains unclear and is being studied further.

Independent data monitoring committees (DMCs) have performed detailed reviews of several studies including the Phase 3, clinical outcomes study in PBC (747-302) and the Phase 3, pivotal study in NASH with fibrosis (747-303). The DMC reviewed data (unmasked for PBC and unblinded by treatment group for NASH with a total of approximately 1000 subjects) in closed sessions, which excluded participation of the Sponsor. Based on these reviews, the DMC recommended that both studies continue without modification.

Post-Marketing Cases in PBC

As of September 2017, greater than 3000 patients have received Ocaliva[®] in the post-marketing setting. In patients with moderate to severe hepatic impairment (Child-Pugh B and C), liver decompensation, liver failure, and death have been reported when Ocaliva was dosed up to 7 times the recommended once weekly starting dose for such patients. Based on the initial medical assessment of these cases, which included patients having undergone liver transplant, there was insufficient evidence suggesting a causal relationship between higher than recommended dosing and the reported adverse events. However, Intercept Pharmaceuticals, Inc. (the Sponsor) continues to assess the potential association between adverse events, including deaths, and the higher than recommended dosing of Ocaliva observed in PBC patients with moderate to severe hepatic impairment (Child-Pugh B and C) through ongoing post-marketing pharmacovigilance activities.

Signs and symptoms reported in patients experiencing liver-related adverse events who received Ocaliva include: increases in bilirubin and other liver enzymes, new or worsening pruritus, new

or worsening fatigue, vague neuropsychiatric symptoms (such as dysphoria), abdominal pain, nausea, vomiting, diarrhea, dehydration, jaundice, and liver decompensation.

Refer to the IB for additional information regarding the known potential risks with the investigational product.

6. STUDY OBJECTIVES AND PURPOSE

The study will be conducted in patients with PBC and moderate to severe hepatic impairment defined as CP-B and CP-C with MELD scores ranging from 6 to 24.

6.1. Primary Objectives

- To evaluate the PK of OCA and its conjugates, glyco-OCA and tauro-OCA, and OCA metabolite glucuronide compared with placebo
- To evaluate the safety and tolerability of OCA treatment compared with placebo

6.2. Secondary Objectives

- To evaluate the effect of OCA treatment compared to placebo on:
 - The MELD score and its components
 - CP score and its components
 - Liver biochemistry including total and direct bilirubin, alkaline phosphatase (ALP), and aminotransferases (alanine aminotransferase [ALT], aspartate aminotransferase [AST], and gamma glutamyl transaminase [GGT]), international normalized ratio (INR), creatinine, albumin, platelets
 - Biomarkers of bile acid synthesis and homeostasis including fibroblast growth factor 19 (FGF-19), 7 α -hydroxy-4-cholesten-3-one (C4), and plasma bile acids

6.3. Additional Objectives

- To evaluate the effect of OCA treatment compared to placebo on:
 - Noninvasive markers of liver fibrosis (Enhanced Liver Fibrosis [ELF]TM score)
 - Noninvasive measurement of liver stiffness (transient elastography [TE])
- To assess the PK/Pharmacodynamic (PD) relationship of OCA with:
 - PK parameters compared to PD parameters and safety and tolerability assessments
- To assess patient reported outcomes (Pruritus Visual Analogue Scale [VAS], PBC-40, EQ 5D-5L, Chronic Liver Disease Questionnaire [CLDQ])

- To assess clinical events consistent with end-stage liver disease
 - Death (all cause)
 - Liver transplant
 - MELD score ≥ 15 (for patients with MELD ≤ 12 at baseline)
 - Hospitalization (as defined by a stay of 24 hours or greater) for new onset or recurrence of: variceal bleed, hepatic encephalopathy (as defined by a West Haven score of ≥ 2), spontaneous bacterial peritonitis
 - Uncontrolled ascites (diuretic resistant ascites requiring therapeutic paracentesis at a frequency of at least twice in a month)
 - Hepatocellular carcinoma (HCC)

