8.2. Patient Inclusion Criteria

1. A definite or probable diagnosis of PBC (consistent with American Association for the Study of Liver Diseases [AASLD] and European Association for the Study of the Liver [EASL] Practice Guidelines [Lindor 2009, EASL 2009]), defined as having ≥ 2 of the following 3 diagnostic factors:
 - History of elevated ALP levels for at least 6 months
 - Positive antimitochondrial antibody (AMA) titer or if AMA negative or low titer ($\leq 1:80$), PBC-specific antibodies (anti-GP210 and/or anti-SP100) and/or antibodies against the major M2 components (PDC-E2, 2-oxo-glutaric acid dehydrogenase complex)
 - Liver biopsy consistent with PBC (collected at any time prior to Screening)
2. Evidence of cirrhosis including at least one of the following:
 - Biopsy results consistent with PBC Stage 4
 - Liver stiffness as assessed by TE Value ≥ 16.9 kPa
 - Clinical evidence in the absence of acute liver failure consistent with cirrhosis including: gastroesophageal varices, ascites, radiological evidence of cirrhosis (nodular liver or enlargement of portal vein and splenomegaly)
 - Combined low platelet count ($< 140\,000/\text{mm}^3$) with:
 - persistent decrease in serum albumin, or
 - elevation in prothrombin time /INR (not due to antithrombotic agent use), or
 - elevated bilirubin ($2 \times \text{ULN}$)
3. Satisfy the criteria of the modified CP classification for hepatic impairment during Screening:
 - Moderate: CP-B (Scores 7 to 9) or
 - Severe: CP-C (Scores 10 to 12)
4. MELD score of 6 to 24 at Screening
5. Age ≥ 18 years
6. Taking UDCA for at least 12 months (stable dose for ≥ 3 months) prior to Day 1, or unable to tolerate or unresponsive to UDCA (no UDCA for ≥ 3 months)
7. Contraception: Female patients must be postmenopausal, surgically sterile, or if premenopausal (and not surgically sterile), be prepared to use ≥ 1 effective method of contraception during the study and for 30 days after the end of treatment visit. Effective methods of contraception are considered to be those listed below:
 - Barrier method, ie, (a) condom (male or female) with spermicide **or** (b) diaphragm with spermicide; or

- Intrauterine device; or
 - Vasectomy (partner); or
 - Hormonal (eg, contraceptive pill, patch, intramuscular implant or injection); or
 - Abstinence, if in line with the preferred and usual lifestyle of the patient (where abstinence is defined as refraining from heterosexual intercourse)

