11. OVERVIEW OF ASSESSMENTS

The assessments supporting the objectives for the study are in Table 7:

Table 7: Table of Assessments

Primary Objectives	Assessments
PK parameters	OCA and its conjugates glyco-OCA and tauro-OCA, and metabolite OCA glucuronide
Safety and tolerability	SAEs and TEAEs, physical exam, ECG, vital signs, clinical laboratory assessments, discontinuations, pruritus, and fatigue
Secondary Objectives	Assessments
Changes in risk scores	Changes in MELD and in CP Scores and components of the CP score and MELD score
Changes in liver biochemistry and hepatobiliary damage	Total and direct bilirubin, ALP, ALT, AST, GGT, INR, creatinine, albumin, platelets
PD parameters	FGF-19, C4, and plasma bile acids
Additional Objectives	Assessments
Noninvasive measurements of liver fibrosis, liver stiffness and cirrhosis	TE/ELF (HA, P3NP, and TIMP-1)
PK/PD relationship	PK parameters compared to PD parameters and safety and tolerability assessments (above)
Patient-reported outcomes	Pruritus VAS, PBC-40, EQ-5D-5L, CLDQ
Clinical events	Death (all-cause and liver-related), liver transplant, MELD score ≥ 15 (for patients with MELD ≤ 12 at baseline), hospitalization for new onset or recurrence of: variceal bleed, hepatic encephalopathy, spontaneous bacterial peritonitis, uncontrolled ascites, and HCC.

ALP = alkaline phosphatase; ALT = alanine aminotransferase; AST = aspartate aminotransferase; C4 = 7 α -hydroxy-4-cholesten-3-one; CLDQ = Chronic Liver Disease Questionnaire; CP = Child-Pugh; ECG = electrocardiogram; ELF = enhanced liver fibrosis; FGF-19 = fibroblast growth factor-19; GGT = gamma-glutamyl transferase; HA = hyaluronic acid; INR = international normalized ratio; MELD = Model End Stage Liver Disease; OCA = obeticholic acid; P3NP = procollagen 3 N-terminal peptide; PBC = Primary Biliary Cholangitis; PD = pharmacodynamic; PK = pharmacokinetic; SAE = serious adverse event; TE = Transient Elastography; TEAE = treatment emergent adverse events; TIMP-1 = tissue inhibitor of metalloproteinase 1; VAS = visual analog scale

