15.6. Additional Efficacy Analyses

Analyses of changes in liver stiffness (TE) and liver fibrosis (ELF [HA, P3NP, and TIMP-1]) will be summarized and analyzed using the same methodology specified for the key secondary analyses of change in bilirubin.

The following clinical endpoints will be captured in the study:

- Time to death (all cause)
- Time to liver-related death
- Time to liver transplant
- MELD score ≥ 15 (for patients with MELD ≤ 12 at baseline)
- Hospitalization (as defined by a stay of 24 hours or greater) for new onset or recurrence of:
 - Time to variceal bleed
 - Time to hepatic encephalopathy (as defined by a West Haven score of ≥ 2)

- Time to spontaneous bacterial peritonitis (confirmed by diagnostic paracentesis)
- Time to uncontrolled ascites (diuretic resistant ascites requiring therapeutic paracentesis at a frequency of at least twice in a month).

The incidence and time to first occurrence of any above listed clinical events will be summarized by treatment group using the log rank test stratified by the randomization stratification factor. KM estimates of the distribution of the time-to-event will be tabulated and graphed by treatment group. The tabulation will include the KM methodology using 25th, 50th (median), and 75th percentiles with associated 2-sided 95% confidence intervals (CIs), as well as percentage of censored observations. The number and percent of patients censored and with events will be presented. The hazard ratio and 2-sided 95% CI will be estimated based on a Cox regression model stratified by randomization strata.

In addition, the incidence and time to each of the above clinical events, and the incidence and time to occurrence of hepatocellular carcinoma (HCC) will be summarized by treatment group using the same methods as defined above.

Full details regarding additional efficacy analyses will be detailed in the SAP.

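### Uncontrolled ascites that already meets the definition at entry can count as an on-study event, and the protocol disagrees on whether the event requires hospitalization

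*Protocol*

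**What the plan says.** **Event, as a stand-alone item.** Section 6.3, and the synopsis objectives in the same form, give the event its own bullet beside the hospitalization bullet: "Uncontrolled ascites (diuretic resistant ascites requiring therapeutic paracentesis at a frequency of at least twice in a month"). No baseline restriction is attached.

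**Event, under hospitalization.** Table 7 in section 11, and the Criteria for Evaluation table in the synopsis, instead read "hospitalization for new onset or recurrence of: variceal bleed, hepatic encephalopathy, spontaneous bacterial peritonitis, uncontrolled ascites, and HCC".

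**Analysis.** Section 15.6 lists "Time to uncontrolled ascites (diuretic resistant ascites requiring therapeutic paracentesis at a frequency of at least twice in a month"). It then states "The incidence and time to first occurrence of any above listed clinical events will be summarized by treatment group using the log rank test". That test, and a Cox model for the hazard ratio, both use the Child-Pugh strata. Each event is also analysed singly by the same methods.

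**Eligibility.** Section 8.2 accepts as evidence of cirrhosis "Clinical evidence in the absence of acute liver failure consistent with cirrhosis including: gastroesophageal varices, ascites, radiological evidence of cirrhosis". Section 8.3 has 13 exclusions. They cover current encephalopathy, hepatorenal and hepatopulmonary syndrome, active infection including peritonitis, and known or suspected liver cancer. None covers refractory ascites or regular paracentesis.

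**A neighbouring component.** The MELD event is restricted by baseline status: "MELD score ≥ 15 (for patients with MELD ≤ 12 at baseline").

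**The concern.** An incident-event endpoint needs a population at risk. The MELD component has one. Stand-alone uncontrolled ascites does not, although patients who already satisfy it may enrol. For such a patient, paracentesis simply continuing at the same rate after Day 1 fits the wording within about a month. In the time-to-first-event analysis that patient then has an early event unrelated to progression, and a later death, transplant or bleed adds nothing to the composite.

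The second problem is independent of the first. Twice-monthly paracentesis done as an outpatient is an event under section 6.3 and a non-event under a literal reading of Table 7. The same patient's outcome then depends on which page is followed.

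**Working it through.** No figure in the protocol is in dispute. The sample size of 50 (30 + 20) is justified by pharmacokinetics plus an allowance for safety and efficacy, and does not depend on this endpoint. The check is therefore mainly a comparison of texts.

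**Step 1. Setting of the event.**

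| Place | Hospitalization required? | New onset or recurrence required? |
|---|---|---|
| Synopsis objectives; 6.3 | No, own bullet | No |
| Synopsis evaluation table; Table 7 | Yes, read literally | Yes, read literally |
| Synopsis analysis list; 15.6 | Not settled | Not settled |

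In the last row the item follows the hospitalization sub-items. The indentation could not be read reliably in the text available, so nothing is rested on it. The clinical criterion (diuretic resistance, paracentesis at least twice in a month) is the same wherever it is spelled out. The conflict concerns setting and onset.

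**Step 2. Can a patient meet the criterion at entry?** Ascites counts towards inclusion (8.2). Moderate to severe ascites scores 3 points in Table 12, within an admitted Child-Pugh range of 7 to 12. No exclusion applies (8.3). So yes.

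**Step 3. Does another rule stop such a patient counting?** Section 15.9 limits adjudication to suspected events after the first dose. Continuing paracenteses do occur after the first dose, and no rule in the protocol tells adjudicators to reject them.

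**Step 4. Illustrative size.** The prevalence *q* of uncontrolled ascites at entry is not in the protocol, so the range is an assumption. With 50 patients, 25 per arm:

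- expected cases at entry = 50*q*
- P(at least one) = 1 − (1 − *q*)^50
- P(arms differ by 2 or more) from two independent binomials of size 25
- risk ratio if all entry cases count and the true risks in the others are 20% and 40% (also assumed) = [*q* + (1 − *q*)0.2] / [*q* + (1 − *q*)0.4], against a true 0.50

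| *q* | Expected | P(at least one) | P(difference ≥ 2) | Risk ratio |
|---|---|---|---|---|
| 2% | 1 | 64% | 12% | 0.52 |
| 5% | 2.5 | 92% | 31% | 0.56 |
| 10% | 5 | 99.5% | 47% | 0.61 |
| 20% | 10 | about 100% | 59% | 0.69 |

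**Step 5. Chance imbalance.** Suppose 5 of 50 qualify at entry. Ignoring strata, P(4:1 or 5:0, either direction) = 2[C(25,4)·C(25,1) + C(25,5)] / C(50,5) = 2(316,250 + 53,130) / 2,118,760 = 0.35. If all 5 were among 10 Child-Pugh C patients randomized 5:5, it is 2(25 + 1)/252 = 52/252 = 0.21.

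Cox fits were simulated with no treatment effect, a 30% event risk at 48 weeks (assumed) and entry cases given an event near Week 4. The median hazard ratio is about 1.0 with no entry cases, about 1.4 at a 4:1 split and about 1.8 at 5:0. The reverse 4:1 split gives about 1/1.39 = 0.72. Events number about 5 + 45 × 0.30 = 18.5, so SE(log HR) ≈ 2/√18.5 = 0.47. A shift to 1.39 is then ln(1.39)/0.47 ≈ 0.7 standard errors.

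**The case against.** - **Adjudication and documents not shown.** Sections 14.2.3 and 15.9 require confirmation by a blinded committee before any analysis. The charter holds the event definitions, and section 15.6 leaves full details to the SAP. Either could contain a baseline rule. This stands: it supports *can count*, not *counts*. It does not remove the point, because the protocol states the definition itself and does so inconsistently.
- **Ordinary ascites.** A reader might infer that any ascites present at entry becomes an outcome. It does not. Only diuretic-resistant ascites needing paracentesis at least twice in a month meets the definition.
- **Loose drafting.** The run-on in the two tables also sweeps in liver cancer, which section 6.3 lists separately, so it may be punctuation rather than intent. That is plausible, but it is current text in the table linking objectives to assessments and has to be reconciled.
- **Later events.** A reader might infer that later deaths and transplants are lost. They are hidden only in the composite; section 15.6 analyses each event separately as well.
- **Comparators.** The hospitalized events accept recurrence, so prior disease does not take patients out of risk there. Only the MELD component is a true baseline restriction.
- **Bias in the hazard ratio.** The values 1.4 and 1.8 show one direction of a chance imbalance. Over repeated randomizations with no treatment effect the median remains 1.0, and stratification by Child-Pugh class, of which ascites is a component, removes part of the imbalance. What remains under a true effect is the dilution in Step 4.

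**Conclusion.** The point holds in two parts. The stand-alone definition has no baseline condition while patients who already meet it are eligible, so uncontrolled ascites at entry can be counted as an on-study event. Separately, the protocol conflicts with itself on whether hospitalization is needed, which leaves outpatient cases undetermined.

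The documents do not support saying that such cases certainly will count, or that the composite hazard ratio is biased by a known amount. Every number in Steps 4 and 5 rests on an assumed prevalence and assumed event risks.

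Practical impact is limited. This is one component of an additional objective in a study that section 5.4.1 says is not designed to evaluate clinical outcomes formally, and section 15 plans no formal hypothesis testing. It is still worth correcting. The same section plans a meta-evaluation with Study 747-302, and section 5.4.4 justifies the placebo group partly as a comparator for clinical events.

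**What to change.** 1. Use one definition in the synopsis, section 6.3, Table 7 and section 15.6. In Table 7 and the synopsis evaluation table, move uncontrolled ascites and hepatocellular carcinoma out of the hospitalization list, matching section 6.3 and the synopsis objectives.
2. Count uncontrolled ascites as an event only in patients who did not meet the definition in the month before Day 1. Patients who did meet it stay at risk for every other component.
3. Take baseline status from the Screening medical history and the Day 1 procedures record, and add a field for paracenteses in the month before Day 1. The Day 1 record reaches back only to Screening, 14 to 28 days, so it does not reliably cover a month.
4. Put the same rule in the adjudication charter.

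**Cost.** Wording changes in four places, one eCRF field and slightly fewer composite events. The event definition in Study 747-302 should be checked first, because a rule applied here alone could weaken the planned meta-evaluation.
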